#### 5.4 SCREEN FAILURES

Screen failures are defined as participants who consent to participate in the clinical trial but are not subsequently entered in the study and receive study intervention. A minimal set of screen failure information is required and includes demography, screen failure details, eligibility criteria, and any serious adverse event (SAE).

Individuals who do not meet the criteria for participation in this trial (screen failure) may have certain assessments repeated (e.g. laboratory results, ECG, vital signs, etc.) based on the investigator's judgment. Rescreened participants should be assigned the same participant number as for the initial screening.

#### 5.5 STRATEGIES FOR RECRUITMENT AND RETENTION

### 5.5.1 PARTICIPANT RECRUITMENT

Participants may be identified in the following ways:

- submission of information into a Second Opinion Program Portal;
- a call into the IBTC Phase 0 navigator or other research staff in regard to the study;
- as an existing patient at Barrow Brain and Spine (BBS) and/or Investigator Institution and has been identified as a possible study participant at a clinic visit or is reviewed at Tumor Board and recommended to be screened for an IBTC trial;
- other recruitment strategies identified.

#### 5.5.1.1 SECOND OPINION PROGRAM PORTAL

Second Opinion Programs are standard practice and potential participants may submit to the portal in order to consult with the neurosurgeons and obtain their opinion on the potential participant's diagnosis or proposed treatment. Potential participants who submit information to the IBTC Second Opinion Portal also receive a consent form to be included in the Subject Recruitment Database.

#### 5.5.1.2 EXISTING PATIENT(S)

Potential participants may be identified in the course of the participant's medical record review and the neurosurgeon may recommend consideration for the trial. At that time, the Phase 0 navigator or other research staff may contact the potential participant via phone, email or letter. Study specific phone scripts, email or letters may be developed for each study and submitted to the IRB for review and approval prior to use.

#### 5.5.1.3 CALLS WITH RESEARCH STAFF

Potential participants may find information regarding the clinical trials via media advertisements or word-of-mouth and call the Phase 0 Navigator or another research team member. The research team will utilize the IRB-approved phone script to guide the conversation. If there is follow-up contact via mail or email, an IRB-approved template should be utilized.

### 5.5.2 PRE-SCREENING ACTIVITIES

Pre-screening activities may be utilized to assess potential participants for inclusion in studies prior to obtaining consent if the procedures are performed as part of the practice of medicine and which would be done whether or not study entry was contemplated ([FDA 1998](#)).

#### 5.5.2.1 INFORMATION GATHERED DURING PRE-SCREENING

Information not available through a medical record review may be obtained during a pre-screening discussion with the potential participant either in person or via the telephone prior to informed consent. The pre-screening questions in the IRB-approved script will be suitable and appropriate to address specific inclusion/exclusion criteria and other study specific details to ascertain the participant's ability to participate in the trial. The discussion may not strictly adhere to the script; however, the script and/or consent form will provide a guide for the discussion. The information obtained will be limited to the minimum necessary to determine screening eligibility.

A Phase 0 Study of Infigratinib in Recurrent Glioblastoma Patients  
Protocol 2020-08

The following activities will not be considered acceptable pre-screening activities (if not part of the standard clinical visit) and will not be completed until the participant has signed the consent form.

- Staff asking participants to wash-out from medications or fast prior laboratory testing;
- Staff obtaining complete medical histories, physical exams, laboratory testing and other screening assessments.

---

### 5.5.3 CONFIDENTIALITY PARTICIPANT INFORMATION AND CONFIDENTIALITY

Potential participants may provide private information and medical records from non-covered entities. A separate authorization to release and review medical records will be obtained from the participant to allow the institution to request the information from a non-covered entity to determine eligibility.

The institution will not retain identifying information about potential participants that:

- ✓ are not existing patients and;
- ✓ have not provided verbal consent to be recorded in an IRB-approved participant recruitment database and;
- ✓ are pre-screened for a study but do not enroll.

For these participants, any pre-screening documents with identifying information gathered prior to obtaining consent and prior to enrollment may also be retained in research files but must have segments containing identifiable information blacked out as soon as it is determined the individual will not be enrolled, or adhere to institutional guidelines and policies.

## 6 STUDY INTERVENTION

### 6.1 STUDY INTERVENTION(S) ADMINISTRATION

#### 6.1.1 STUDY INTERVENTION DESCRIPTION

**Table 1** Study Interventions

Study treatments	Pharmaceutical form and route of administration	Dosage Strength	Form	and	Frequency and/or Regimen
Phase 0	(7-day regimen)				
infigratinib	Capsule for oral use	100mg capsules	+	25mg	QD
Expansion Cohort (optional)	(21-day regimen, 28-day cycle)				
infigratinib	Capsule for oral use	100mg capsules	+	25mg	QD for 21 days

#### 6.1.2 DOSING AND ADMINISTRATION

In Phase 0, the dose for infigratinib will be 125 mg oral (PO), taken QD over 7 days on Day 1 through Day 7. The last dose will be given on the morning of Day 7, approximately 7-9 hours prior to craniotomy for tumor resection. Day 1 and Day 7 doses will be taken in the clinic. Days 2-5 will be taken at home. Day 6 will be taken at home or in clinic (Table 2).

**Table 2** Phase 0 Dose Schedule

Study Intervention	infigratinib
Day 1	125 mg In Clinic
Day 2	125 mg At Home
Day 3	125 mg At Home
Day 4	125 mg At Home
Day 5	125 mg At Home
Day 6	125 mg At Home or Clinic
Day 7	125 mg In Clinic

In the Expansion Cohort, the dose for infigratinib will be 125 mg oral (PO) QD on Days 1 through 21 in a 28-day cycle. On days with a trough PK sample, the doses will be administered in clinic, if possible (Cycle 1 & 2, Days 1, 8, and 15). A delay of a cycle due to holiday, weekend, bad weather, or other unforeseen

A Phase 0 Study of Infigratinib in Recurrent Glioblastoma Patients  
Protocol 2020-08

circumstances will be permitted for a maximum of 7 days and not counted as a protocol deviation. The reason for the treatment interruption should be documented on the CRF. A cycle begins when study treatment is dispensed for the cycle and administered. Thus, if an expected cycle start is delayed, the number of days in the current cycle is increased beyond 28 days. A visit window of  $\pm 1$  day in Cycle 1 and 2 on Days 1, 8, and 15 and  $\pm 3$  days in Cycle 3 onward is allowed.

A participant may continue to receive study treatment until confirmed progressive disease, unacceptable toxicity, or discontinuation for any other reason.

Participants should be instructed to take the daily dose of infigratinib in the morning in a fasted state at least at least 1 hour before or 2 hours after a meal. Infigratinib should be taken at approximately the same time each day (24  $\pm$  2 hours interval). Subjects should be instructed to swallow the capsules whole, i.e., without chewing, with a glass of water (~250 mL), which should be consumed over as short a time as possible.

If vomiting occurs after ingestion of a daily dose, no re-dosing of the participant should occur before the next scheduled dose. Also, if a dose cannot be administered early in the day, that dose should not be made up later that day, and dosing should resume the following day.

---

#### 6.1.3 DOSE MODIFICATIONS

In Phase 0, there are no dose modifications. If a participant is unable to tolerate the dose, the participant will be discontinued. The Expansion Phase dose adjustments are discussed below.

**Table 3 Dose adjustments for infigratinib-related toxicity**

Worst Toxicity CTCAE v5.0 Grade (unless otherwise specified)	Recommended Dose Modifications any time during a cycle of therapy
Cardiac disorders	
Cardiac - Prolonged QTcF interval Grade 1 and 2 : QTcF $\geq$ 481msec and $\leq$ 500 msec (asymptomatic)	Maintain dose level of infigratinib ECG assessments should be performed for 2 additional cycles at the same frequency as in cycle 1, or as clinically indicated 

• If ECG assessments show no QTcF <math>\geq</math> 481 msec, for subsequent cycles ECG monitoring will be performed as per visit schedule.

• If ECG assessments are still abnormal (QTcF

○ <math>\geq</math> 481 msec and <math>\leq</math> 500 msec), then ECG

○ Monitoring must continue at the same frequency as in cycle 1 for all subsequent cycles.

A Phase 0 Study of Infigratinib in Recurrent Glioblastoma Patients

Protocol 2020-08

Worst Toxicity CTCAE v5.0 Grade (unless otherwise specified)	Recommended Dose Modifications any time during a cycle of therapy
Grade 3 : QTcF > 500msec as identified on the ECG by the investigator	
Hold infigratinib.
 
 
Monitor patient with hourly ECGs until the QTcF has returned to baseline.
 
Perform further monitoring as clinically indicated.
 
Exclude other causes of QTcF prolongation such as hypokalemia, hypomagnesaemia and decreased blood oxygenation.
 
Patients should receive appropriate electrolyte replacement and should not receive further infigratinib until electrolytes are documented to be within normal limits.
 
 
Once the QTcF prolongation has resolved and if the QTcF prolongation was confirmed by the central reader, patients may be re-treated at one lower dose level at the investigator's discretion
 
 
ECG assessments should be performed for 2 additional cycles at the same frequency as in cycle 1 or as clinically indicated 
 
If ECG assessments show no QTcF <math>\geq</math> 481 msec, for subsequent cycles ECG monitoring will be performed as per visit schedule.
 
If ECG assessments are still abnormal (QTcF <math>\geq</math> 481 msec and <math>\leq</math> 500 msec), then ECG monitoring must continue at the same frequency as in cycle 1 or as clinically indicated, for all subsequent cycles
 
 
 
Patients who experience recurrent QTcF <math>\geq</math> 500msec after one dose reduction will be discontinued from study.
 
 
NB: If ventricular arrhythmia or Torsades de Pointes is observed in a patient, he/she will be discontinued from the study.

Cardiac disorders - others Grade $\geq$ 3, or congestive heart failure $\geq$ 2	Discontinue patient from study treatment.
Investigations-Hematology	

A Phase 0 Study of Infigratinib in Recurrent Glioblastoma Patients  
 Protocol 2020-08

Worst Toxicity CTCAE v5.0 Grade (unless otherwise specified)	Recommended Dose Modifications any time during a cycle of therapy
ANC decreased (Neutropenia) Grade 3 (ANC < 1.0 - 0.5 x 10  /L)	Hold dose of infigratinib until resolved to CTCAE Grade ≤ 1 or baseline, then 
 
• If resolved in ≤ 7 days, maintain dose level of infigratinib
 
• If resolved in > 7 days, ↓ 1 dose level of infigratinib.
 

Grade 4 (ANC < 0.5 x 10  /L)	Hold dose of infigratinib until resolved to CTCAE ≤ Grade 1, ↓ 1 dose level of infigratinib.
Febrile neutropenia Grade 3 (ANC < 1.0 x 10  /L, single temperature of > 38.3°C or a sustained temperature of ≥ 38.0°C)	Hold dose of infigratinib until resolved to CTCAE Grade ≤ 1, then 
 
• If resolved by ≤ 7 days, ↓ 1 dose level of infigratinib.
 
• If not resolved within 7 days discontinue patient from study drug treatment.
 

Grade 4	Discontinue patient from study treatment.
Hemoglobin Grade 3 (<8.0 mg/dL – 6.5 mg/dL)	Hold dose of infigratinib until resolved to CTCAE Grade ≤ 1 or baseline, then maintain dose level
Grade 4 (< 6.5 mg/dL)	Hold dose of infigratinib until resolved to CTCAE Grade ≤ 1 or baseline, then ↓ 1 dose level.
Platelet count decreased (Thrombocytopenia) Grade 3 (PLT < 50 - 25 x 10  /L) without bleeding	Hold dose of infigratinib until resolved to CTCAE Grade ≤ 1 or baseline 
 
• If resolved in ≤ 7 days, maintain dose level of infigratinib.
 
• If resolved in > 7 days, ↓ 1 dose level of infigratinib.
 

Grade 3 (PLT < 50 - 25 x 10  /L) with bleeding or Grade 4 (PLT < 25 x 10  /L )	Hold dose of infigratinib until resolved to CTCAE Grade ≤ 1 or baseline, then ↓ 1 dose level
Investigations – Renal	

A Phase 0 Study of Infigratinib in Recurrent Glioblastoma Patients  
 Protocol 2020-08

Worst Toxicity CTCAE v5.0 Grade (unless otherwise specified)	Recommended Dose Modifications any time during a cycle of therapy
Serum creatinine Grade 1 and Pi >5.5 mg/dL and/or tCa x Pi >55 mg  /dl  and despite phosphorus lowering therapy for at least 14 days	See Table 4 Hold dose of infigratinib until resolved to CTCAE Grade ≤ 1 or baseline 
 
• If resolved in ≤ 7 days, maintain dose level of infigratinib.
 
• If resolved in > 7 days, ↓ 1 dose level of infigratinib.
 

Grade 2 (> 1.5 - 3.0 x ULN)	Hold dose of infigratinib until resolved to CTCAE Grade ≤ 1 or baseline 
 
• If resolved in ≤ 7 days, maintain dose level of infigratinib.
 
• If resolved in > 7 days, ↓ 1 dose level of infigratinib.
 

Grade 2 and Pi >5.5 mg/dL and/or tCa x Pi >55 mg/dl and despite phosphorus lowering therapy for at least 14 days or Grade ≥ 3 (> 3.0 x ULN)	Discontinue patient from study treatment.
Investigations – Hepatic	
Blood bilirubin (patients with Gilbert Syndrome these dose modifications apply to changes in direct bilirubin only) Grade 2 (>1.5 – 3.0 x ULN)	Hold dose of infigratinib until resolved to CTCAE Grade ≤ 1 
 
• If resolved in ≤ 7 days, maintain dose level of infigratinib.
 
• If resolved in > 7 days, ↓ 1 dose level of infigratinib.
 

Grade ≥ 3 (> 3.0 x ULN)	Discontinue patient from study treatment Note: If CTCAE Grade 3 or 4 hyperbilirubinemia is due to hemolysis, then ↓ 1 dose level of infigratinib and continue treatment at the discretion of the Investigator.

A Phase 0 Study of Infigratinib in Recurrent Glioblastoma Patients  
 Protocol 2020-08

Worst Toxicity CTCAE v5.0 Grade (unless otherwise specified)	Recommended Dose Modifications any time during a cycle of therapy
AST or ALT Grade 3 ( $> 5.0 - 20.0 \times \text{ULN}$ ) without bilirubin elevation $> 2.0 \times \text{ULN}$	Hold dose of infigratinib until resolved to CTCAE Grade $\leq 1$ or baseline 
 
• If resolved in <math>\leq 7</math> days, maintain dose level of infigratinib.
 
• If resolved in <math>> 7</math> days, <math>\downarrow 1</math> dose level of infigratinib.
 

Grade 4 ( $> 20.0 \times \text{ULN}$ ) without bilirubin elevation $> 2.0 \times \text{ULN}$	Discontinue patient from study treatment
AST or ALT and Bilirubin AST or ALT $> 3.0 - 5.0 \times \text{ULN}$ and total bilirubin $> 2.0 \times \text{ULN}$ without liver metastasis or evidence of disease progression in the liver	Hold dose of infigratinib until resolved to CTCAE Grade $\leq 1$ 
 
• If resolved in <math>\leq 7</math> days, <math>\downarrow 1</math> dose level of infigratinib.
 
• If resolved in <math>> 7</math> days, discontinue patient from study treatment.
 

AST or ALT $> 5.0 \times \text{ULN}$ and total bilirubin $> 2.0 \times \text{ULN}$	Discontinue patient from study treatment
Laboratory / Metabolic disorders	
Asymptomatic amylase and/or lipase elevation Grade 3 ( $> 2.0 - 5.0 \times \text{ULN}$ )	
 
• Hold dose of infigratinib until resolved to CTCAE Grade <math>\leq 2</math>.
 
• <math>\downarrow 1</math> dose level of infigratinib
 
 
Note: A CT scan or other imaging study to assess the pancreas, liver, and gallbladder must be performed within 1 week of the first occurrence of any CTCAE <math>\geq</math> Grade 3 amylase and/or lipase.
 
If asymptomatic CTCAE Grade 2 elevations of lipase and/or amylase occur again at the reduced dose, patients will be discontinued permanently from study treatment.

Grade 4 ( $> 5.0 \times \text{ULN}$ )	Discontinue patient from study treatment
Hyperphosphatemia Serum phosphorus $> 5.5 - 7.0 \text{ mg/dL}$	See Table 4 Maintain dose level of infigratinib, but modify phosphate lowering therapy

A Phase 0 Study of Infigratinib in Recurrent Glioblastoma Patients

Protocol 2020-08

Worst Toxicity CTCAE v5.0 Grade (unless otherwise specified)	Recommended Dose Modifications any time during a cycle of therapy
Serum phosphorus >7.0 – 10.0 mg/dL despite phosphate lowering therapy	
Hold infigratinib dose until resolved to serum phosphorus <math>\leq</math> 5.5 mg/dL
 
 
if resolved by <math>\leq</math> 14 days after suspending infigratinib, <math>\downarrow</math> 1 dose level
 
if does not resolve within 14 days of suspending infigratinib, discontinue patient from the study.
 

Serum Pi $>$ 10.0 mg/dL	Discontinue patient from study treatment
Hypercalcemia Serum calcium grade 2	Hold infigratinib dose until resolved to grade 1 or baseline: 
 
if resolved <math>\leq</math> 7 days after suspending infigratinib, maintain dose level
 
if resolved <math>></math> 7 days after suspending infigratinib, <math>\downarrow</math> 1 dose level
 

Serum calcium $\geq$ grade 3	Discontinue patient from the study
Nervous system disorders	
Neurotoxicity Grade 2	Omit dose of infigratinib until resolved to CTCAE Grade $\leq$ 1, then $\downarrow$ 1 dose level of infigratinib
Grade $\geq$ 3	Discontinue patient from study drug treatment
GI disorders	
Pancreatitis Grade $\geq$ 2	Discontinue patient from study drug treatment
Diarrhea Grade 1	Maintain dose level of infigratinib, but initiate anti-diarrheal treatment  Note: Antidiarrheal medication is recommended at the first sign of abdominal cramping, loose stools or overt diarrhea. See 6.4.1.3.1

A Phase 0 Study of Infigratinib in Recurrent Glioblastoma Patients  
 Protocol 2020-08

Worst Toxicity CTCAE v5.0 Grade (unless otherwise specified)	Recommended Dose Modifications any time during a cycle of therapy
Grade 2	
Hold dose of infigratinib until resolved to CTCAE Grade <math>\leq 1</math>
 
 
Optimize anti-diarrheal treatment, maintain dose level of infigratinib.
 
For reoccurrence of diarrhea CTCAE Grade 2, hold dose of infigratinib until resolved to CTCAE Grade <math>\leq 1</math>, <math>\downarrow</math> infigratinib by 1 dose level
 

Grade 3	
 
Hold dose of infigratinib until resolved to CTCAE Grade <math>\leq 1</math>
 
Optimize anti-diarrheal treatment
 
<math>\downarrow</math> infigratinib by 1 dose level
 
For reoccurrence of diarrhea CTCAE Grade 3, despite optimal anti-diarrheal treatment, discontinue patient from study treatment.
 

Grade 4	Discontinue patient from study treatment.
Vomiting Grade 2 not controlled by optimal anti-emetic therapy	Hold infigratinib doses until $\leq$ grade 1, $\downarrow$ 1 dose level
Grade 3 not controlled by optimal anti-emetic therapy or Grade 4	Discontinue patient from study
Eye Disorders (confirmed by ophthalmologic examination)	
Retinal disorders Grade 2 CSR and CSR-like events	Hold infigratinib until resolved to $\leq$ grade 1 but refer the patient to a retinal specialist for evaluation 
 
If resolved in <math>\leq 14</math> days, <math>\downarrow</math> infigratinib by 1 dose level
 
If resolved in <math>> 14</math> days, discontinue infigratinib
 

Grade 3 CSR and CSR-like events and any other grade 3 eye disorders	Hold infigratinib until resolved to grade $\leq 1$ . 
 
If resolved in <math>\leq 14</math> days, <math>\downarrow</math> infigratinib by 1 dose level
 
If resolved in <math>> 14</math> days, discontinue infigratinib
 

$\geq$ grade 1 retinal vein occlusion, grade 4 CSR and CSR-like events, and grade 4 other eye disorders	Discontinue infigratinib

A Phase 0 Study of Infigratinib in Recurrent Glioblastoma Patients  
Protocol 2020-08

Worst Toxicity CTCAE v5.0 Grade (unless otherwise specified)	Recommended Dose Modifications any time during a cycle of therapy
Other ocular/visual toxicity	
≥ grade 3	Hold infigratinib until resolution to ≤ grade 1 If resolution in ≤14 days, ↓ 1 dose level, otherwise discontinue infigratinib
General disorders	
Fatigue Grade 3	Hold dose of infigratinib until resolved to CTCAE Grade ≤ 1 
 
• If resolved in ≤ 7 days, maintain dose level of infigratinib.
 
• If resolved in > 7 days, discontinue patient from study treatment.
 

Other clinically significant AEs	
Grade 3	Hold dose of infigratinib until resolved to CTCAE Grade ≤ 1, then ↓ 1 dose level of infigratinib.
Grade 4	Discontinue patient from study treatment

All dose modifications should be based on the worst preceding toxicity. Once a dose has been reduced it will not be increased at a later time even if there is no toxicity. Patients who require more than two dose reductions of infigratinib will be discontinued from study drug treatment.
 
If a patient requires a dose delay of > 14 days from the intended day of the next scheduled dose of infigratinib then study treatment must be stopped.
	

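### Table 3: the hold for Grade 1 creatinine with uncontrolled phosphorus is released as soon as it starts, and for Pi ≤7.0 mg/dL no other mandatory rule replaces it

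*Combined protocol and SAP*

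**What the plan says.** Dose modifications apply only in the Expansion Cohort (section 6.1.3). The relevant texts are these.

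- **Table 3, Grade 1 creatinine row, entry:** "Grade 1 and Pi >5.5 mg/dL and/or tCa x Pi >55 mg" (units mg²/dL²), with the qualifier "and despite phosphorus lowering therapy for at least 14 days".
- **Same row, action:** "Hold dose of infigratinib until resolved to CTCAE Grade ≤ 1 or baseline". The row also points to Table 4.
- **Same row, dose on restart:** the instruction for early resolution is "If resolved in ≤ 7 days, maintain dose level of infigratinib". Resolution later than that means a reduction of one level.
- **Grade 2 creatinine:** the same release text. With the same phosphorus condition, treatment is discontinued.
- **Hyperphosphatemia, Pi >5.5-7.0 mg/dL:** "Maintain dose level of infigratinib, but modify phosphate lowering therapy".
- **Hyperphosphatemia, Pi >7.0-10.0 mg/dL despite therapy:** "Hold infigratinib dose until resolved to serum phosphorus" ≤5.5 mg/dL, then reduce, or discontinue if this takes more than 14 days. Above 10.0, discontinue.
- **Table 3 footer:** "All dose modifications should be based on the worst preceding toxicity".
- **Table 4:** requires a phosphorus-driven hold only above 7.0 mg/dL. It follows participants until phosphorus reaches 5.5 mg/dL or below, baseline, or stability. Raised creatinine with hyperphosphatemia is repeated at least weekly until it resolves, alongside 24-hour urine.
- **Section 6.4.1.3.3:** accepts Grade 1 creatinine as good enough to resume. It also permits, without requiring, an interruption to normalize phosphorus and calcium, followed by a lower dose.

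**The concern.** A hold rule needs a release that is false when the hold begins. Here the entry grade lies inside the release grade, so the rule cannot keep anyone off drug. The values that made the row apply, phosphorus and the calcium-phosphorus product, are missing from the release.

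This is the intermediate safeguard on a renal risk. Section 6.4.1.3.3 reports serious renal events with infigratinib, including renal failure and acute kidney injury. One creatinine grade higher, the same phosphorus condition ends treatment. If the Grade 1 step does nothing, the plan goes from unchanged dose straight to permanent discontinuation. The row can also be read in more than one way, so up to 3 sites could manage the same participant differently.

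**Working it through.** The plan gives no figure to reproduce. The check sets the entry and release conditions side by side, looks for another rule that closes the gap, and sizes what remains.

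**1. Entry against release**
- Entry: creatinine = Grade 1, and (Pi >5.5 or tCa × Pi >55), after at least 14 days of therapy.
- Release: creatinine Grade ≤1, or baseline.
- Grade 1 satisfies Grade ≤1, so release is true on day 0 and the branch for resolution within 7 days applies: same dose.
- The reduction branch is unreachable. While creatinine stays at Grade 1 the hold is already released; if it rises to Grade 2, the Grade 2 rows take over.

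The other Table 3 holds with a grade-based release let go at a grade below their trigger, for example Grade 3 to ≤1, Grade 2 to ≤1, or amylase/lipase Grade 3 to ≤2. The Grade 2 creatinine row uses the same release words, and there they work.

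**2. Does another mandatory rule cover the participant?**

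| Serum Pi (mg/dL) | Phosphorus rule in Table 3 | Gap closed? |
|---|---|---|
| >10.0 | Discontinue | Yes |
| >7.0-10.0 despite therapy | Hold to ≤5.5, then reduce or discontinue | Yes |
| >5.5-7.0 | Keep dose, change binder | No |
| ≤5.5 with product >55 | None | No, unless calcium itself is Grade 2 or higher |

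The worst-toxicity footer brings the stricter rows into play above 7.0, so no gap is claimed there. Below that, Table 4's 5.5 mg/dL target governs follow-up, not restart. Section 6.4.1.3.3 also accepts Grade 1 creatinine, and its interruption is optional. Table 4 treats Grade 1 creatinine with hyperphosphatemia as still unresolved, whereas the Table 3 row citing it treats Grade 1 as resolved.

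**3. Can the product limit be exceeded with Pi ≤7.0?** Assume tCa is total (corrected) calcium; the row does not define it, and total corrected calcium is named only in inclusion criterion 12. Calcium needed = 55 / Pi:
- Pi 7.0: 55/7.0 = 7.86 mg/dL
- Pi 6.0: 55/6.0 = 9.17 mg/dL
- Pi 5.5: 55/5.5 = 10.0 mg/dL
- Example below 5.5: 10.5 × 5.3 = 55.65

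So the product criterion can be met where no hyperphosphatemia row applies.

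**4. Time to the next scheduled serum phosphorus.** Table 4 starts phosphorus-lowering therapy at C1D1. The Schedule of Activities places expansion chemistry on Day 1 of each cycle, and section 6.4.1.3.3 adds a first-week phosphorus and calcium check. The first scheduled chemistry that can satisfy the 14-day condition is therefore C2D1. The weekly repeats in Table 4 name creatinine and urine, not serum phosphorus or calcium. If dosing resumes on C2D1, up to 21 doses precede C3D1: 21 × 125 mg = 2,625 mg.

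**5. Population.** 20 Phase 0 participants (section 9.1) × 50% (section 9.2) = 10 expected in expansion.

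**The case against.** The strongest reply is that no sensible clinician would end a hold the moment it began. The row sends the reader to Table 4, which names a phosphorus target, so resolution may be taken to mean clearing the combined condition. That may well happen in practice. But the row joins its two creatinine targets with an *or*, gives no phosphorus or product threshold, and cites a table whose target is for follow-up.

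The 21-dose figure is also open to challenge. Table 4 cannot follow participants to a phosphorus value, or adjust sevelamer by phosphorus band, without measuring it. Section 6.4.1.3.3 asks for careful electrolyte monitoring. Participants attend for blood draws on C2D8 and C2D15, and Table 9 puts phosphorus and calcium in the same panel as creatinine. A participant triggering at C2D1 has also just had 7 days off drug, so the abnormality must have survived that week. These points stand as limits on likelihood and size: 21 doses is a worst case, not a typical exposure.

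The band is mild by the protocol's own standards, and Grade 1 creatinine may be an intended resume level. That could justify its place in the release, but not the omission of phosphorus and the product from a hold that they trigger.

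Backstops also exist: weekly creatinine and 24-hour urine, renal ultrasound as indicated, discontinuation at Grade 2 with the same condition, the hypercalcemia row, the Safety Officer route and the advisory heading of Table 3. They limit the consequence without correcting the rule.

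**Conclusion.** The concern holds. As written, the Grade 1 creatinine row provides no effective hold, and its reduction branch cannot be reached. The gap is confined to Pi >5.5-7.0 mg/dL, or product >55 mg²/dL² with Pi ≤7.0; at Pi ≤5.5 a calcium of Grade 2 or higher would bring in the hypercalcemia row.

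This is a stated safety rule that fails when followed, so it should be corrected, though the scale is small. About 10 participants are expected in expansion, no event rate is given, and no number affected can be claimed. The 21-dose exposure assumes resumption on C2D1 and no unscheduled tests. The calcium thresholds rest on the assumed meaning of tCa. No effect on PFS6 is claimed.

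**What to change.** Amend three places:

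1. **Table 3, Grade 1 creatinine row.** Hold until Pi ≤5.5 mg/dL and tCa × Pi ≤55 mg²/dL², with creatinine at Grade ≤1 or baseline. If met within 7 days keep the dose; if later, reduce one level. Define tCa.
2. **Section 6.4.1.3.3.** Align the resume condition, and settle whether restart is at the same dose (as in Table 3) or a lower one (as this section says for its optional interruption).
3. **Table 4, renal entry.** Repeat serum phosphorus and calcium with the weekly creatinine.

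Both limits are already in the plan: 5.5 is the release in the Pi >7.0-10.0 row, and 55 is this row's own trigger. The medical lead should decide the final values.

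The cost is one table row, one sentence and one phrase, plus a few unscheduled phosphorus and calcium tests drawn with creatinine already required. No new participants or visit types are needed. The clinical downside is longer holds for a few participants. Some could reach the existing rule that after a delay of more than 14 days "from the intended day of the next scheduled dose of infigratinib then study treatment must be stopped".

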**Adequate hepatic and renal function:**

total bilirubin  $\leq 1.5 \times \text{ULN}$ .

Participants with Gilbert's syndrome with a total bilirubin  $\leq 2.0$  times ULN and direct bilirubin within normal limits are permitted.

AST(SGOT)  $\leq 3 \times \text{institutional ULN}$

ALT(SGPT)  $\leq 3 \times \text{institutional ULN}$

Calculated or measured creatinine clearance  $\geq 45 \text{ mL/min}$

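### Table 3 gives two different re-dosing instructions for bilirubin above 3.0 × ULN with AST/ALT above 3.0 to 5.0 × ULN that resolves within 7 days, and no text expressly ranks the two rows

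*Combined protocol and SAP*

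**What the plan says.** All of the relevant rules are in Section 6.1.3. They apply to the Expansion Cohort, because Phase 0 allows no dose modification.

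- **Bilirubin row, Grade 3 or worse (above 3.0 × ULN).** The action is discontinuation, with one note: "Discontinue patient from study treatment Note: If CTCAE Grade 3 or 4 hyperbilirubinemia is due to hemolysis", the dose goes down one level and the site may "continue treatment at the discretion of the Investigator". There is no condition on AST or ALT. The row heading adds that for "patients with Gilbert Syndrome these dose modifications apply to changes in direct bilirubin only". Such participants can be enrolled: Section 5.1 admits Gilbert syndrome with total bilirubin up to 2.0 × ULN if "direct bilirubin within normal limits are permitted".
- **Combined row.** The trigger is "AST or ALT $> 3.0 - 5.0 \times \text{ULN}$ and total bilirubin $> 2.0 \times \text{ULN}$ without liver metastasis" or liver progression. The action is to hold until Grade 1 or better. If that takes 7 days or less, the dose drops one level; if it takes more than 7 "days, discontinue patient from study treatment". Bilirubin has a floor of 2.0 × ULN and no ceiling.
- **General wording.** The trigger column is headed "Worst Toxicity CTCAE v5.0 Grade (unless otherwise specified"), and the footer says "All dose modifications should be based on the worst preceding toxicity".
- **Other routes.** Questions about dose reduction go to the IBTC Safety Officer. Below 75 mg the default is discontinuation, unless a further reduction is discussed with the Safety Officer because of clinical benefit.

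**The concern.** The rows that deal with AST/ALT alone are limited to cases without bilirubin above 2.0 × ULN, so they cannot overlap the combined rows. The bilirubin rows carry no matching limit. One participant can therefore meet a row that ends treatment and a row that allows a restart, on the same day and on the same laboratory results.

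What is at stake is re-exposure after a combined rise in bilirubin and transaminases. Up to 3 sites will apply the table, and they could answer differently. The liver retest trigger in Section 6.1.3 (ALT 5 × ULN with total bilirubin 2 × ULN, or ALT 8 × ULN) is not met while ALT stays below 5 × ULN, so it would not bring this case to attention.

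**Working it through.** The plan states no figure to reproduce. The check sets the rows side by side.

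**Where the triggers meet.** The bilirubin row needs bilirubin above 3.0 × ULN. The combined row needs bilirubin above 2.0 × ULN and AST/ALT above 3.0 to 5.0 × ULN. Both hold when bilirubin is above 3.0 × ULN and AST/ALT is above 3.0 to 5.0 × ULN. The participant must also have no liver metastasis or progression (otherwise the combined row is off), no hemolysis, and no Gilbert syndrome with normal direct bilirubin (otherwise the bilirubin row does not order a stop).

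**Outcomes at example values**, no hemolysis or Gilbert syndrome:

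| Bilirubin (× ULN) | ALT (× ULN) | Resolved | Bilirubin row | Combined AST/ALT-and-bilirubin rows |
|---|---|---|---|---|
| 3.5 | 2 | either | discontinue | none applies |
| 3.5 | 4 | 7 days or less | **discontinue** | **resume one level lower** |
| 3.5 | 4 | more than 7 days | discontinue | discontinue |
| 3.5 | 6 | either | discontinue | discontinue |
| 2.5 | 4 | 7 days or less | same dose | one level lower |
| 2.5 | 4 | more than 7 days | one level lower | discontinue |
| 2.5 | 6 | 7 days or less | same dose | discontinue |
| 2.5 | 6 | more than 7 days | one level lower | discontinue |

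The second line is the conflict. If the combined row alone were followed at bilirubin 3.5 × ULN with quick recovery, the action would run discontinue, resume, discontinue as ALT goes from 2 to 4 to 6. Added transaminase injury would soften the action in the middle band.

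**By dose.** At 125 mg the choice is stop or resume at 100 mg. At 100 mg it is stop or resume at 75 mg. At 75 mg a further reduction means discontinuation by default, so the rows agree.

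**Full grid.** Take three groups (neither condition; Gilbert with normal direct bilirubin; hemolytic), bilirubin 1.8, 2.5 and 3.5, ALT 2, 4 and 6, two recovery times and three doses: 3 × 3 × 3 × 2 × 3 = 162 combinations. The discontinuation for Grade 3 or worse clashes with the combined row in 2 of them: the bold line at 125 mg and at 100 mg. The values were picked to hit each band and carry no probabilities, so 2 of 162 is not a frequency.

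**Other unranked overlaps.** The lines at bilirubin 2.5 also differ, as do hemolytic cases at bilirubin 3.5 with ALT 4 and recovery beyond 7 days (continue at a reduced dose, or discontinue). In these the combined row is the stricter one. Only in the bold line is it the milder one.

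**Size of the group.** Section 9.2 expects 50% of the Phase 0 cohort in the expansion: 0.5 × 20 = 10 participants. The documents give no rate for this liver pattern, so no expected count can be stated.

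**The case against.** The strongest reply is that the text already decides the case. The bilirubin row is an unconditional stop with hemolysis as its exception and a Gilbert limitation; a concurrent ALT rise is neither. The column heading and the footer both point to the worst toxicity, which here is the bilirubin of Grade 3 or worse. In the 2.0 to 3.0 × ULN band the combined row is stricter at both recovery times, so the natural pattern is that the stricter row governs, and above 3.0 × ULN that again means stopping. The irregular ALT sequence arises only if a row the participant plainly meets is ignored.

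Much of this stands. The better reading is discontinuation. What remains is that neither the heading nor the footer addresses overlapping rows, and the combined row is written in ULN multiples without a grade, so worst grade does not rank it. It is also the more specific description of the participant, and a site can follow it as written.

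The reply also says that the consequence is small. That is right. Participants enter with bilirubin at or below 1.5 × ULN and AST/ALT at or below 3 × ULN, both rows stop dosing at once, and a restart needs recovery to Grade 1 or better within 7 days. The actions are headed as recommendations, the investigator may withdraw a participant for a laboratory abnormality, and a DSMB oversees safety. The Safety Officer route helps only if the site notices the overlap.

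A reader might infer that the protocol directs re-treatment after severe combined liver injury. The documents do not support that, since one applicable row orders a stop and the general wording leans the same way.

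**Conclusion.** The inconsistency is real and narrow. For bilirubin above 3.0 × ULN with AST/ALT above 3.0 to 5.0 × ULN, resolved within 7 days, in a participant on 125 mg or 100 mg without hemolysis, Gilbert syndrome, liver metastasis or liver progression, two stated safety rules give opposite re-dosing instructions. The general wording favors discontinuation without expressly settling it.

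It is low-stakes and should be rare in a cohort of about 10, and it does not touch endpoints, sample size or analysis. It is worth correcting at the next amendment because it concerns re-exposure after liver injury and the correction is simple. The conclusion assumes that the rows are read as printed and that 75 mg is the lowest dose under the default rule. How often a site would choose the milder row cannot be judged from the documents.

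**What to change.** Add one line to the hepatic block of Table 3: *If more than one hepatic row applies, follow the most restrictive action; bilirubin above 3.0 × ULN (direct bilirubin in Gilbert syndrome) not due to hemolysis means discontinue, whatever the AST/ALT.*

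The first half also settles the overlaps at bilirubin above 2.0 to 3.0 × ULN and in hemolytic cases, which a sentence about bilirubin above 3.0 × ULN alone would leave open. The line keeps the Gilbert rule and the combined row's hold. Capping the combined row at 3.0 × ULN would be a poorer repair: with ALT at 4 × ULN, Gilbert participants with normal direct bilirubin would be left with no hepatic row, and hemolytic cases would lose the hold.

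The cost is one line of text, with no added visits, tests or participants; Table 9 already collects direct bilirubin when total bilirubin is Grade 2 or worse. The downside is that a few participants who recover quickly would be discontinued rather than resumed at a lower dose, which the bilirubin row already requires. Hemolytic cases that meet a stricter combined row would likewise follow that row.
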